8.1.6. Electronic Case Report Forms

Designated investigator staff will enter the data required by the protocol into the eCRF using fully validated secure web-enabled software that conforms to US CFR 21 Part 11 requirements. Designated investigator site staff will not be given access to the system until they have been trained. Subsequent to data entry, a study monitor will perform source data verification within the EDC system. Original entries as well as any changes to data fields will be stored in the audit trail of the system.

Automatic validation procedures within the system check for data discrepancies during and after data entry and, by generating appropriate error messages, allow the data to be confirmed or corrected online by the designated investigator site staff. The Investigator must certify that the data entered into the electronic Case Report Forms are complete and accurate.

At the conclusion of the trial, Akero will provide the site with a read-only archive copy of the data entered by that site. This archive must be stored in accordance with the records retention requirements outlined in Section 8.1.5.

8.1.7. Inspections

The investigator will make available all source documents and other records for this trial to Akero's appointed study monitors, to IRB/IEC/EC, or to regulatory authority or health authority inspectors.

8.1.8. Protocol Compliance

The investigator is responsible for ensuring the study is conducted in accordance with the procedures and evaluations described in this protocol.

8.2. Sponsor Responsibilities

8.2.1. Protocol Modifications

Protocol modifications, except those intended to reduce immediate risk to study subjects, may be made only by Akero. The investigator must submit all protocol modifications to the IRB/IEC/EC in accordance with local requirements and receive documented IRB/IEC/EC approval before modifications can be implemented.

8.2.2. Study Report and Publications

A clinical study report (CSR) will be prepared and provided to the regulatory agencies. Akero will ensure that the report meets the standards set out in the ICH Guideline for Structure and Content of Clinical Study Reports (ICH E3). Note that an abbreviated report may be prepared in certain cases.

Investigators in this study may communicate, orally present, or publish in scientific journals or other scholarly media only after the following conditions have been met: the results of the study in their entirety have been publicly disclosed by or with the consent of Akero in an abstract, manuscript, or presentation form or the study has been completed at all study sites for at least 18 months.

The investigator will submit to Akero any proposed publication or presentation along with the respective scientific journal or presentation forum at least 60 days before submission of the publication or presentation.

No such communication, presentation, or publication will include Akero's confidential information (see Section 8.1.4).

The investigator will comply with Akero's request to delete references to its confidential information (other than the study results) in any paper or presentation and agrees to withhold publication or presentation for an additional 60 days in order to obtain patent protection if deemed necessary.

8.3. Joint Investigator/Sponsor Responsibilities

8.3.1. Payment Reporting

Investigators and their study staff may be asked to provide services performed under this protocol (e.g., attendance at Investigator's Meetings). If required under the applicable statutory and regulatory requirements, Akero will capture and disclose to Federal and State agencies any expenses paid or reimbursed for such services, including any clinical trial payments, meal, travel expenses or reimbursements, consulting fees, and any other transfer of value.

8.3.2. Access to Information for Auditing or Inspections

Representatives of regulatory authorities or of Akero may conduct inspections or audits of the clinical study. If the investigator is notified of an inspection by a regulatory authority the investigator agrees to notify the Akero medical monitor immediately. The investigator agrees to provide to representatives of a regulatory agency or Akero access to records, facilities, and personnel for the effective conduct of any inspection or audit.

10. APPENDICES

Appendix A. Schedule of Assessments- Main Study

				On-Treatment Visits ^a											Week	
Assessments ^a	Screening (- 6 wks)	Pre- Baseline ^l (-2 wks)	Baseline Day 1	Week 1	Wks 2 and 3	Week 4	48- 96hrs post- dose	Wks 5, 6 and 7	Week 8	48- 96hrs post- dose	Wks 9, 10, 11, 13, 14, 15	Week 12	Week 16	ЕТ	20 Safety follow -up ^{bb}	Repeat Biopsy Week 22-24°
Clinical Assessments														-	-	
Written Informed Consent	Х															
Eligibility	Х	Х	Х													
Medical History	Х															
Physical Examination ^b	Х		Х	Х		Х			Х			Х	Х	Х	Х	
Vital Signs ^c	Х	Х	Х	Х	Х	Х	Х	Х	Х	Х	Х	Х	Х	Х	Х	
Weight ^w	Х	Х	Х	Х	Х	Х		Х	Х		Х	Х	Х	Х	Х	
Triplicate BP/HR ^d			Х				Х			Х						
Height	Х															
Hip and Waist Circumference ^w	Х		Х	Х		Х			Х			Х	Х	Х	Х	
12-lead ECG	X		Х										Х	Х		
FibroScan®	Xr															
Liver Biopsy	Xe															Х
MRI-PDFF ^s	Xf							\mathbf{X}^{f}				\mathbf{X}^{f}		X ^p		Х
DXA Scan ^t	Х												Х	Х		
AUDIT-C Questionnaire	Х															
On-Study Questionnaires ^g			Х	Х		Х			Х			Х	Х	X ^p		
Lifestyle Modification ^u	Х		Х	Х	Х	Х		Х	Х		Х	Х	Х			
Administer Study Drug ^y			Х	Х	Х	Х		Х	Х		Х	Х				
Concomitant Medications	X	Х	Х	Х	Х	Х	Х	Х	Х	Х	Х	Х	Х	Х	Х	Х
Adverse Events	X ^h	Х	Х	Х	Х	Х	Х	Х	Х	Х	Х	Х	Х	Х	Х	Х

					On-Treatment Visits ^a											Week	
Assessmen	nts ^a	Screening (- 6 wks)	Pre- Baseline ^l (-2 wks)	Baseline Day 1	Week 1	Wks 2 and 3	Week 4	48- 96hrs post- dose	Wks 5, 6 and 7	Week 8	48- 96hrs post- dose	Wks 9, 10, 11, 13, 14, 15	Week 12	Week 16	ЕТ	20 Safety follow -up ^{bb}	Repeat Biopsy Week 22-24°
	Laboratory Assessments																
Chemistry Lipids, Co	y, Hematology, pagulation ⁱ	Х	X ^x	Х	х	Xz	х		Xz	х		Xz	Х	Х	Х	Х	
Serum Sto	orage Sample ^q			Х	Х		Х			X			Х	Х	Х	Х	
Urine dru	g screen ⁱ	Х															
Serologie	s ⁱ	Х															
Endogenc	ous FGF21 ^v			Х													
Enhanced (ELF™)	Liver Fibrosis	Х							Xf				X ^f		Х		
Biomarke	rs ⁱ	X ^{aa}		Х	Х		Х			X			Х	Х	Х	Х	
PK ^j				Х	Х		Х	Х		X	Х		Х	Х	Х	Х	Х
ADA and	NAB ^k			Х			Х			Х				Х	Х	Х	Х
Saliva con	rtisol testing ^m			Х	Х		Х	Х		Х	Х		Х	Х	Х	Х	
Pregnancy	y testing ⁿ	Х		Х			Х			Х			Х	Х	Х	Х	

ADA = anti-drug antibodies; AUDIT-C = alcohol use disorders identification test; BP = blood pressure; DXA = Dual Energy X-ray Absorptiometry;

ECG = electrocardiogram; HR = heart rate; PK = pharmacokinetic; MRI-PDFF = magnetic resonance imaging - proton density fat fraction; NAB = neutralizing antibody

- a All visits after Baseline (Day 1) can be performed within the following window: ± 3 days for weekly visits 1 20. Other windows are indicated below.
- b Complete PE including assessment at Screening, Baseline and Weeks 12 and 16, symptom driven at weeks 1, 4, 8, 20, or ET. CP Score assessments should be completed as part of the physical exam at Baseline, Week 12, Week 16, ET and Week 20.
- c Vitals to include systolic and diastolic BP, pulse, respiration rate, and oral temperature (at Screening and Baseline only) will be collected at each visit.
- d Triplicate BP/HR at Baseline and at 48 96 hours post-dose on Weeks 4 and 8 to correspond to C_{max}. BP/HR to be measured in same arm with at least two minutes rest between measurements.
- e Liver biopsy obtained within 180 days of randomization to confirm eligibility.
- f MRI-PDFF and ELFTM will be performed during screening, at Weeks 6 and 12 ± 5 days. Corrected T1 will be collected, where available.
- g If the Baseline questionnaires are missed at Day 1, questionnaires should not be collected at the remaining timepoints. The following questionnaires will be administered: HRQoL include: SF-36, CLDQ-NAFLD, WPAI. It is recommended that the questionnaires be completed prior to any study procedures being performed and prior to the subject seeing a health care provider.
- h AE reporting during screening is limited to SAEs and AEs related to study procedures.
- i Refer to Table 3. At visits where CTX-1 or lipids are collected, the samples to be collected in the morning following an overnight fast of at least 8 hours.

- j PK sampling will be obtained pre-dose at all timepoints listed and at 48-96 hours post-dose on weeks 4 and 8 to correspond to C_{max}.
- k Samples will be obtained for detection of ADA against EFX and if required a neutralizing ADA assay will be run on the same sample.
- 1 Pre-baseline labs should be collected 4 weeks post-Screening.
- m Saliva cortisol testing will be obtained pre-dose at all timepoints listed and at 48 96 hours post-dose on Weeks 4 and 8 to correspond to C_{max}.
- n For female subjects of childbearing potential only. Serum pregnancy test at screening and urine pregnancy test at other time points.
- o Subjects with \geq 30% relative fat reduction on MRI-PDFF at Week 12 will be required to return at Week 22 24 for a repeat liver biopsy and MRI-PDFF. The biopsy and MRI-PDFF should be collected within 5 working days of one another. The window for this visit is - 6 weeks.
- p At the discretion of the Investigator.
- q Serum storage samples banked for possible additional clinical testing.
- r At least 2-3 hours fasting is required prior to all elastography assessments.
- s At least 4 hours fasting is required prior to all MR assessments.
- t DXA scan should include lumbar spine, femoral neck, and total hip with Subjects in the standard (supine) position. Total body composition may also be collected at the DXA timepoints, where available, to determine body fat distribution.
- u All subjects will receive counseling regarding lifestyle modifications including the maintenance of a healthy diet and participation in regular exercise at the Baseline Visit. At each subsequent visit, subjects will be asked if there has been a significant change in diet, or physical activity.
- v Endogenous FGF21 serum sample to be collected in the morning following an overnight fast of at least 8 hours.
- w Weight, waist and hip circumference should be obtained by the same study personnel between visits for each subject to minimize variability in the measurement. On dosing days, weight will be collected pre-dose. Weight should be obtained using a calibrated scale. The subject should be weighed in consistent clothing.
- x Only confirmatory ALT/AST to be collected at the Pre-Baseline Visit to confirm eligibility. Pre-Baseline labs may not be repeated if inclusion criteria is not met.
- y Administration of study drug should occur following all other study procedures and sample collection for that visit.
- z Glucose only to be measured. Sample should be collected at the end of the study visit.
- aa HbA1c only to be measured.
- bb The Safety Follow-up visit should be performed 4 weeks following the last dose of study drug. For subjects who complete the study, this will be Week 20. Subjects who terminate the study early should have this visit 4 weeks following the last dose of study drug received.

								On-Treat	ment Visit	s ^a					
Assessments ^a	Screening (- 6 wks)	Pre- Baseline ¹ (-2 wks)	Baseline Day 1	Week 1	Wks 2 and 3	Week 4	48- 96hrs post- dose	Wks 5, 6 and 7	Week 8	48- 96hrs post- dose	Wks 9, 10, 11, 13, 14, 15	Week 12	Week 16	ET	Week 20 Safety follow-up ^z
Clinical Assessm	ents														•
Written Informed Consent	Х														
Eligibility	Х	Х	Х												
Medical History	Х														
Physical Examination ^b	Х		Х	Х		Х			Х			Х	Х	Х	Х
Vital Signs ^c	Х	Х	Х	Х	Х	Х	Х	Х	Х	Х	Х	Х	Х	Х	Х
Weight ^w	Х	Х	Х	Х	Х	Х		Х	Х		Х	Х	Х	Х	Х
Triplicate BP/HR ^d			Х				Х			Х					
Height	Х														
Hip and Waist Circumference ^u	X		Х	х		х			Х			Х	х	Х	Х
12-lead ECG	Х		Х										Х	Х	
FibroScan®	Xq												Xq		
Liver Biopsy	Xe												X ^{aa}		
DXA Scan ^r	Х												Х	Х	
AUDIT-C Questionnaire	Х														
On-Study Questionnaires ^g			Х	Х		Х			Х			Х	Х	Xº	
Lifestyle Modification ^s	Х		Х	Х	Х	Х		Х	Х		Х	Х	Х		
Administer Study Drugw			Х	Х	Х	Х		Х	Х		Х	Х			
Concomitant Medications	Х	Х	Х	Х	Х	Х	Х	Х	Х	Х	Х	Х	Х	Х	Х
Adverse Events	\mathbf{X}^{h}	Х	Х	Х	Х	Х	Х	Х	Х	Х	Х	Х	Х	Х	Х
Laboratory Asse	ssments														
Chemistry, Hematology, Lipids, Coagulation ⁱ	Х	X ^v	х	X	Xx	X		Xx	Х		X ^x	Х	Х	Х	Х
Serum Storage Sample ^p			Х	Х		Х			Х			Х	Х	Х	Х

Appendix B.Schedule of Assessments- Cohort C

				On-Treatment Visits ^a											
Assessments ^a	Screening (- 6 wks)	Pre- Baseline ^l (-2 wks)	Baseline Day 1	Week 1	Wks 2 and 3	Week 4	48- 96hrs post- dose	Wks 5, 6 and 7	Week 8	48- 96hrs post- dose	Wks 9, 10, 11, 13, 14, 15	Week 12	Week 16	ET	Week 20 Safety follow-up ^z
Urine drug screen ⁱ	Х														
Serologies ⁱ	Х														
Endogenous FGF21 ^t			Х												
Enhanced Liver Fibrosis (ELF TM)	Х							Xf					Х	Х	
Biomarkers ⁱ	Ху		Х	Х		Х			Х			Х	Х	Х	Х
PK ^j			Х	Х		Х	Х		Х	Х		Х	Х	Х	Х
ADA and NAB ^k			Х			Х			Х				Х	Х	Х
Saliva cortisol testing ^m			Х	Х		Х	Х		Х	Х		Х	Х	Х	Х
Pregnancy testing ⁿ	Х		Х			Х			Х			Х	Х	Х	Х

ADA = anti-drug antibodies; AUDIT-C = alcohol use disorders identification test; BP = blood pressure; DXA = Dual Energy X-ray Absorptiometry;

ECG = electrocardiogram; HR = heart rate; PK = pharmacokinetic; NAB = neutralizing antibody

a All visits after Baseline (Day 1) can be performed within the following window: ± 3 days for weekly visits 1 - 20. Other windows are indicated below.

b Complete PE including assessment at Screening, Baseline and Weeks 12 and 16, symptom driven at weeks 1, 4, 8, 20, or ET. CP Score assessments should be completed as part of the physical exam at Screening, Baseline, Week 12, Week 16, ET and Week 20.

c Vitals to include systolic and diastolic BP, pulse, respiration rate, and oral temperature (at Screening and Baseline only) will be collected at each visit.

- d Triplicate BP/HR at Baseline and at 48 96 hours post-dose on Weeks 4 and 8 to correspond to C_{max}. BP/HR to be measured in same arm with at least two minutes rest between measurements.
- e Historical liver biopsy obtained within 24 months of screening required to confirm eligibility. If a historical biopsy is not available within 24 months of Screening, the subject may undergo a liver biopsy to confirm eligibility.
- f ELFTM will be performed during screening, at Weeks 6 and 16 ± 5 days.
- g If the Baseline questionnaires are missed at Day 1, questionnaires should not be collected at the remaining timepoints. The following questionnaires will be administered: HRQoL include: SF-36, CLDQ-NAFLD, WPAI. It is recommended that the questionnaires be completed prior to any study procedures being performed and prior to the subject seeing a health care provider.
- h AE reporting during screening is limited to SAEs and AEs related to study procedures.
- i Refer to Table 3. At visits where CTX-1 or lipids are collected, the samples to be collected in the morning following an overnight fast of at least 8 hours.
- j PK sampling will be obtained pre-dose at all timepoints listed and at 48-96 hours post-dose on weeks 4 and 8 to correspond to C_{max}.
- k Samples will be obtained for detection of ADA against EFX and if required a neutralizing ADA assay will be run on the same sample.
- 1 Pre-baseline labs should be collected 4 weeks post-Screening.
- m Saliva cortisol testing will be obtained pre-dose at all timepoints listed and at 48 96 hours post-dose on Weeks 4 and 8 to correspond to C_{max}.
- n For female subjects of childbearing potential only. Serum pregnancy test at screening and urine pregnancy test at other time points.
- o At the discretion of the Investigator.

- Serum storage samples banked for possible additional clinical testing.
- q At least 2-3 hours fasting is required prior to all elastography assessments.
- r DXA scan should include lumbar spine, femoral neck, and total hip with Subjects in the standard (supine) position. Total body composition may also be collected at the DXA timepoints, where available, to determine body fat distribution.
- s All subjects will receive counseling regarding lifestyle modifications including the maintenance of a healthy diet and participation in regular exercise at the Baseline Visit. At each subsequent visit, subjects will be asked if there has been a significant change in diet, or physical activity.
- t Endogenous FGF21 serum sample to be collected in the morning following an overnight fast of at least 8 hours.
- u Weight, waist and hip circumference should be obtained by the same study personnel between visits for each subject to minimize variability in the measurement. On dosing days, weight will be collected pre-dose. Weight should be obtained using a calibrated scale. The subject should be weighed in consistent clothing.
- v Only confirmatory ALT/AST to be collected at the Pre-Baseline Visit to confirm eligibility. Pre-Baseline labs may not be repeated if inclusion criteria is not met.
- w Administration of study drug should occur following all other study procedures and sample collection for that visit.
- x Glucose only to be measured. Sample should be collected at the end of the study visit.
- y HbA1c only to be measured.
- z The Safety Follow-up visit should be performed 4 weeks following the last dose of study drug. For subjects who complete the study, this will be Week 20. Subjects who terminate the study early should have this visit 4 weeks following the last dose of study drug received.
- aa Subjects will be given the option to collect an end of treatment biopsy. Biopsy should be taken within 2-4 weeks of last dose of EFX.

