3.4. Early Termination

If a subject discontinues study drug, every attempt should be made to perform the Early Termination (ET) assessments and the Safety Follow-up assessments. The Safety Follow-up assessments should be completed 4 weeks after the last dose of study drug.

Subjects with ongoing clinically significant clinical or laboratory findings will be followed until the finding is resolved or medically stable; reasonable attempts will be made to follow-up with subjects. The subject's participation will end once all study assessments and follow-up has been completed.

The ET and Safety Follow-up assessments are outlined in the Schedule of Assessments (Appendix A and Appendix B).

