7.7.3. Laboratory Evaluations

Selected laboratory data will be summarized (n, mean, SD, median, minimum, and maximum) by treatment group and study visit along with the corresponding change from baseline values.

Graded laboratory abnormalities will be defined using the grading scheme in the CTCAE. Grading of laboratory abnormalities for analysis purposes will be defined in the Statistical Analysis Plan.

The incidence of treatment-emergent laboratory abnormalities, defined as values that increase at least one toxicity grade from baseline at any time post baseline up to and including the date of last dose of study drugs plus 30 days, will be summarized by treatment group. If baseline data are missing, then any graded abnormality (i.e., at least a Grade 1) will be considered treatment-emergent.

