### 2.2 Study Design

#### 2.2.1 Overview

This is a Phase 2a, randomized, double-blind, placebo-controlled study evaluating the safety and efficacy of EFX in subjects with NASH.

Cohort C will enroll approximately 30 subjects with biopsy-proven NASH. All subjects in Cohort C will have F4 fibrosis. Subjects meeting the study's entry criteria will be randomly assigned in a 1:2 ratio into 2 treatment groups as shown in the figure below:

There will be no stratification for Cohort C. Study drug will be administered subcutaneously once weekly (QW) for a total of 16 weeks. After 16 weeks of treatment, a safety follow-up visit will occur at Week 20. Following 16 weeks of treatment, subjects will be given the option to collect an end of treatment biopsy.

This study will be conducted at approximately 30 sites in the U.S. Additional sites may be added, depending on subject accrual rates.

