### 3.3.7 Study Drug Exposure and Compliance

Weeks of exposure to study drug will be calculated as:

(date of last dose of study drug - date of first dose of study drug + 1) / 7

Weeks of exposure to study drug will be summarized by treatment based on the Safety Set with descriptive statistics and with counts and percentages of subjects with exposure in the following categories:

- >0 to ≤4 weeks
- >4 to ≤8 weeks
- >8 to ≤12 weeks
- >12 to ≤16 weeks
- >16 weeks

The total number of injections administered will be calculated for each subject. A contingency table will be provided to display the number and percentage of subjects in each treatment group with the following number of injections: 1-3, 4-6, 7-9, 10-12, 13-15, >=16.

Subjects that miss 2 or more doses of study drug over the course of study participation are considered noncompliant. The frequency and percentage of subjects who are compliant and noncompliant will be summarized by treatment group.

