	Neutrophil count decreased	<lln -="" 1500="" mm3;
<lln -="" 1.5="" 10e9="" l<="" td="" x=""><1500 - 1000/mm3; <1.5 - 1.0 x 10e9 /L	<1000 - 500/mm3; <1.0 - 0.5 x 10e9 /L	<500/mm3; <0.5 x 10e9 /L	</lln></lln>	<1500 - 1000/mm3; <1.5 - 1.0 x 10e9 /L	<1000 - 500/mm3; <1.0 - 0.5 x 10e9 /L	<500/mm3; <0.5 x 10e9 /L
	White blood cell decreased	<lln -="" 3000="" mm3;
<lln -="" 10e9="" 3.0="" l<="" td="" x=""><3000 - 2000/mm3; <3.0 - 2.0 x 10e9 /L	<2000 - 1000/mm3; <2.0 - 1.0 x 10e9 /L	<1000/mm3; <1.0 x 10e9 /L	</lln></lln>	<3000 - 2000/mm3; <3.0 - 2.0 x 10e9 /L	<2000 - 1000/mm3; <2.0 - 1.0 x 10e9 /L	<1000/mm3; <1.0 x 10e9 /L
	Platelet count decreased	<lln -="" 75,000="" mm3;
<lln -="" 10e9
/L</lln></lln>	<75,000 - 50,000/mm3; <75.0 - 50.0 x 10e9 /L	<50,000 - 25,000/mm3; <50.0 - 25.0 x 10e9 /L	<25,000/mm3; <25.0 x 10e9 /L
Coagulation	INR increased	>1.2 - 1.5;	>1.5 - 2.5;	>2.5;	
		>1 - 1.5 x baseline if on anticoagulation	>1.5 - 2.5 x baseline if on anticoagulation	>2.5 x baseline if on anticoagulation	
		•	•	•	•

For the other parameters, the incidence of abnormalities (as defined by normal ranges) prior to the first dose of study drug and after the first dose of study drug will be summarized with counts and percentages of subjects.

The incidence of treatment-emergent laboratory abnormalities, defined as values that increase at least one toxicity grade from baseline at any time post baseline up to and including the date of last dose of study drugs plus 30 days, will be summarized with counts and percentages of subjects by treatment group. If baseline data are missing, then any graded abnormality (i.e., at least a Grade 1) will be considered treatment-emergent. If no pre-treatment laboratory value is available, the baseline value will be assumed to be normal (i.e., no grade [Grade 0]) for the summary of graded laboratory abnormalities.

Evaluation of drug-induced serious hepatotoxicity (eDISH) plot will be provided to display peak serum ALT and Total Bilirubin (TB) levels for each subject. The peak serum AST versus TB levels for each subject will also be provided.

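### The Safety Follow-up footnotes treat 4 weeks after the last dose and Week 20 as the same date; for completers Week 20 is 5 weeks after it, past the 30-day laboratory cut-off

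*Protocol*

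**What the plan says.** Footnote z in Protocol Appendix B (Cohort C) places the Safety Follow-up visit "performed 4 weeks following the last dose of study drug. For subjects who complete the study, this will be Week 20". Footnote bb in Appendix A (Main Study) makes the same equation: "For subjects who complete the study, this will be Week 20". For subjects who stop early, Protocol 3.4 says the follow-up assessments "should be completed 4 weeks after the last dose of study drug".

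In both schedules the study drug row is marked at Day 1 and at every week from 1 to 15. It is blank at Week 16.

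Protocol 3.1 (Main Study), Protocol 3.3 (both parts) and SAP 2.2.1 (Cohort C) put the visit at Week 20. The SAP wording is "After 16 weeks of treatment, a safety follow-up visit will occur at Week 20". SAP 3.5.2 lists that visit as a collection point for chemistry, hematology and coagulation.

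A laboratory value counts as treatment-emergent if it rises by at least one toxicity grade. Protocol 7.7.3 limits the period: "up to and including the date of last dose of study drugs plus 30 days, will be summarized by treatment group". SAP 3.5.2 uses the same limit: "at any time post baseline up to and including the date of last dose of study drugs plus 30 days". Protocol 7.3.2 and 7.7 and SAP 3.2.2 and 3.5 apply the same 30 days to safety summaries in general.

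**The concern.** The footnotes give a completer two different dates for one visit, and a site with an on-time last dose cannot meet both. The choice of date also decides whether the sample counts. At 28 days the follow-up sample is nominally inside the 30-day laboratory rule; at 35 days it is outside.

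For a completer seen at Week 20, the last scheduled sample in the treatment-emergent count is then Week 16, 7 days after the last dose. For an early terminator it is the follow-up visit, 28 days after. A grade increase first seen at follow-up is counted or left out according to whether the subject completed treatment. Safety is the primary objective of Cohort C, and with about 30 subjects a single graded event is visible in the table.

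**Working it through.** **Inputs**

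- First dose is Day 1 (SAP 3.1.1), so Week w is Day 7w + 1.
- SAP 3.1.2 target days agree: Week 15 = Day 106, Week 16 = Day 113, Week 20 = Day 141.
- Doses are at Day 1 and Weeks 1-15 (dosing rows, Appendices A and B): 1 + 15 = 16 doses, the last on Day 106.
- The visit window is ±3 days (footnote a, both schedules).
- The laboratory cut-off is last dose + 30 days, inclusive.

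**1. The plan's own figure.** The footnotes imply 28 days from last dose to Week 20. That is reproduced only if a dose is given at Week 16: 141 − 113 = 28. It would be a 17th dose, and the dosing row has none there. From the scheduled last dose, 141 − 106 = 35 days.

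**2. The two dates**

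| Half of the footnote | Target | ±3-day window |
|---|---|---|
| 4 weeks after last dose | 106 + 28 = Day 134 | Days 131-137 |
| Week 20 | Day 141 | Days 138-144 |

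The windows do not overlap.

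**3. Against the cut-off.** 106 + 30 = Day 136.

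- Visit at Week 20, last dose on time: the gap is 138 − 106 = 32 to 144 − 106 = 38 days. None of the 7 window days is inside.
- Visit at Week 20, dose also allowed ±3 days (Days 103-109): the gap is 138 − 109 = 29 to 144 − 103 = 41 days. It is 30 or less in 3 of 49 combinations: dose Day 108 with visit Day 138, and dose Day 109 with visit Day 138 or 139.
- Visit 28 days after the last dose, assuming the same ±3 days: the gap is 25-31 days, and 6 of 7 window days are inside.

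**4. What else reports Week 20.** SAP 3.5.2 grades 10 chemistry + 6 hematology + 1 coagulation = 17 terms.

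- Seven have a Week 20 ANCOVA: ALT, AST, bilirubin, ALP, GGT and INR (SAP 3.4.2.1), and platelets (SAP 3.4.2.9).
- That leaves 17 − 7 = 10 terms. CD4 lymphocytes are graded but are not in Protocol Table 3, so no scheduled sample can be lost. Hemoglobin is graded twice, as anemia and as an increase. So 10 − 1 − 1 = 8 scheduled analytes have no named Week 20 ANCOVA: creatinine, CPK, potassium, amylase, glucose, hemoglobin, neutrophils and white cells.

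**5. Adverse events.** The 30-day TEAE clock is the same for every subject. For a completer seen on Day 141, onsets on Days 137-141 fall outside the TEAE rows. The SAE and death rows in SAP 3.5.1 are not restricted to treatment-emergent events.

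**The case against.** **The loss depends on which half of the footnote a site follows.** This stands. A site that goes by 4 weeks after the last dose draws the sample near Day 134, usually inside the cut-off. Because SAP 3.1.2 takes scheduled visits as recorded on the CRF, the sample would still be analysed as Week 20. The exclusion follows only if the visit is held at Week 20, as the body text of both documents says.

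**The SAP does not confirm the dose count.** This also stands. SAP 3.3.7 tabulates subjects "with the following number of injections: 1-3, 4-6, 7-9, 10-12, 13-15, >=16", and the top class is open-ended. The same section has an exposure class above 16 weeks. Its formula gives 106/7 = 15.1 weeks with the last dose at Week 15, and 113/7 = 16.1 with a Week 16 dose. The count of 16 rests on the dosing rows, which agree with weekly dosing for 16 weeks.

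**A 30-day cut-off is defensible.** Largely true. The Phase 1a mean half-life was 3.14-3.38 days, so 30 days is about nine half-lives. Protocol 1.6 does report significant triglyceride and HDL-C effects at 70 mg weekly through Day 57. It calls Day 43 three weeks after the final dose, so that dose was on Day 22 and Day 57 is 35 days later. These are lipid effects at a higher dose than Cohort C's 50 mg and are not evidence of late toxicity. The weakness is that the cut-off and the visit schedule do not fit together.

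**A reader might infer that Week 20 safety data are lost.** The documents do not support that. All individual data are listed (SAP 3.1.4), seven graded terms have Week 20 ANCOVAs, and the eDISH plot states no cut-off. SAP 3.5.2 summarises laboratory values at each planned post-baseline visit, although the general sentence in SAP 3.5, read strictly, stops at 30 days. The ANCOVAs compare means, however, and do not show who moved up a grade.

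**A reader might also infer bias between EFX and placebo.** That is not shown. Completers in both arms lose the same sample. A distortion would need differential discontinuation, and the documents give no rate for this trial. An early terminator's follow-up sample is not guaranteed either, since Protocol 3.4 asks only for every attempt.

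**Conclusion.** The inconsistency is real and needs correcting, but it is minor. On both dosing rows, Week 20 is 35 days after a completer's last dose, not 28, and the two visit windows do not overlap. If the visit is held at Week 20 after an on-time Week 15 dose, the follow-up sample is outside the treatment-emergent graded laboratory count on all 7 window days. An early terminator's 28-day sample nominally counts.

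In Cohort C this concerns one sample, in one summary, for up to about 30 subjects (10 placebo, 20 EFX). Outside the ANCOVAs it affects eight scheduled analytes.

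The conclusion assumes no dose at Week 16, as the schedules show, and that sites follow the Week 20 half of the footnote. The 6-of-7 figure for early terminators also assumes that ±3 days applies to their visit. The Main Study footnote has the same error, but its SAP is not among the documents, so the effect on its tables cannot be checked.

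**What to change.** - **Footnotes z and bb:** 4 weeks after the last dose for subjects who stop early; Week 20, which is 5 weeks after the last dose, for completers. It would help to state in Protocol 5.2.2 that there are 16 injections, the last at Week 15.
- **Protocol 7.7.3 and SAP 3.5.2:** count treatment-emergent laboratory abnormalities through the scheduled Safety Follow-up visit, or last dose plus 30 days if later.
- **Protocol 7.3.2 and 7.7, SAP 3.2.2 and 3.5:** add the matching exception to the general 30-day sentences, so that the by-visit summaries clearly include Week 20.

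The TEAE definition and the 30-day recording limit in Protocol 6.21 stay as they are. If the Main Study SAP repeats the 7.7.3 rule, it needs the same clause.

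The cost is wording only, with no extra visit, sample or dose. There is a downside. A completer's follow-up sample is taken 7 days later than an early terminator's (35 against 28) and 5 days beyond the 30-day TEAE clock, or up to 11 days beyond it at the 41-day extreme. A Day 141 laboratory change could then count as treatment-emergent when an AE with onset that day would not. The report should say so.

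The alternative is to see every subject 28 days after the last dose, which is Day 134 (Week 19) for completers. That keeps one 30-day rule but needs the Week 20 visit and its ±3-day window changed in the protocol.
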